2.3. Chart/Records/Data Review (retrospective and/or prospective)

2.3.1. Provide the planned or approximate number of charts/records/data to be accessed

2.3.1.1. CMCVAMC

Given our previous experience we anticipate having to screen between 1,600-2,000 charts to identify 492 poorly controlled diabetic veterans and 206 mentors who will be eligible and willing to participate.

Similarly we expect to screen 1000 additional charts to identify 206 mentors who are eligible and willing to participate, as well as mentors to replace those who withdraw.

2.3.1.2. Other site

2.3.2. Does this protocol employ an Honest Broker? YES NO

2.3.2.1. If yes, provide name of individual.

2.3.2.2. If no, explain who will access the charts/records.

2.3.2.3. Describe from what database charts/records/data will be accessed.

- 3. **Future Use of Data and Re-Contact**, if applicable. N/A
 - 3.1. If any of the participant's data are going to be retained after the study for future research, the following information must be provided to the participant:
 - 3.1.1. Where will the data be stored?
 - 3.1.2. Who will have access to the data?
 - 3.2. If the subject is going to be re-contacted in the future about participating in future research, this must be specified. Describe the circumstances under which the participant would be re-contacted whether within the VA or outside the VA.
 - 3.2.1. If subjects will receive aggregate study results at the end of the study, the informed consent document must contain this information.

4. **Specimen Collection**

- 4.1. Give the source of all specimens and whether they were collected for research, treatment or diagnosis.

Blood will be drawn to assess HbA1c and direct LDL on three-four different occasions for research purposes. Treatment decisions will not be based on results by the research team.

State where specimens will be stored, secured and when discarded.

- 4.2.

Specimens will be drawn by the CMC VA Medical Center lab and disposed of appropriately. We will not be storing blood for future use.

- 4.3. Explain how destruction of samples will be substantiated.

The CMC VA Medical Center lab will handle blood samples in the same way they handle samples for routine clinical care and subject to the oversight of routine clinical care.

N. **Genetic Testing, if applicable N/A**

- 1. Explain if the study is looking for an association between a genetic marker and a specific disease or condition, but at this point it is not clear if the genetic marker has predictive value.
 - 1.1. The uncertainty regarding the predictive value of the genetic marker is such that studies in this category will not involve participant counseling.
 - 1.2. Describe if the study is based on the premise that a link between a genetic marker and a specific disease or condition is such that the marker is clinically useful in predicting the development of that specific disease or condition.
 - 1.3. Will the subject be notified of the results and the provision for genetic counseling?
 - Yes No N/A
 - 1.3.1. If yes, explain further.
 - 1.4. If biological specimens are used in this protocol, please respond to the following questions by checking the appropriate box:

	YES	NO	N/A
a. Does the project involve genetic testing?			
b. Will specimens be kept for future, unspecified use?			
c. Will samples be made anonymous to maintain confidentiality? (Instructions: Note: If there is a link, it is not anonymous. Coding is not anonymous.)			

d. Will specimens be destroyed after the project-specific use is completed?			
e. Will specimens be sold in the future?			
f. Will subjects be paid for their specimens now or in the future?			
g. Will subjects be informed of the results of the specimen testing?			
h. Are there any implications for family members based on specimen testing results? (If yes, they may be participants.)			
i. Will subjects be informed of results obtained from their DNA?			

- 1.5. Will specimens be de-identified? YES NO N/A
 - 1.5.1. If yes, please describe the procedures to be used.
 - 1.5.2. Include at what point in the process the specimens will be de-identified.
- 1.6. Describe what measures will be taken to minimize the following risks from breaches of confidentiality and privacy resulting from participating in **THIS aspect** of the research project:
 - 1.6.1. physical
 - 1.6.2. psychological
 - 1.6.3. financial
 - 1.6.4. social
 - 1.6.5. legal harm

O. Banking of Collected Specimens

- 1. **Will collected specimens be banked?** YES NO N/A
 - 1.1. **IF BANKING SPECIMENS, IT MUST BE AT AN APPROVED VA REPOSITORY.** (For additional information, refer to VHA Handbook 1200.12, Use of Data and Data Repositories in VHA Research - March 9, 2009.)
 - 1.2. If yes, specify the location where specimens will be banked.
 - 1.2.1. If the location is a non-VA site, has the mandatory approval from the Chief Officer of Research and Development (CRADO) been obtained through submission of a tissue banking application (VA Form 10-0436 - Off-site Application for an Off-site Tissue Banking Waiver)? YES NO N/A
 - 1.2.2. If applicable, attach a copy of the VA Form 10-0436
 - 1.3. Explain how destruction of banked samples will be substantiated.

P. Subject Recruitment (characteristics of the study population)

- 1. **Provide the planned or targeted enrollment at:**
 - 1.1. CMCVAMC - 492 poorly controlled diabetic veterans and 206 mentors, as well as mentors to replace those who withdraw.
 - 1.2. Other sites -
 - 1.3. Not applicable; chart review or use of previously collected data -
- 2. **Screening and/or Eligibility Requirements**
 - 2.1. Describe and provide justification for:
 - 2.1.1. Inclusion criteria

All participants and mentors will be type 2 diabetics. To be eligible they must have developed diabetes after the age of 30. To ensure that we are targeting those most likely to benefit from improving control we enroll diabetics with persistently poor DM control. Persistently poor DM control will be defined as having an HbA1c > 8% on 2 different occasions in the course of 24 months, with at least 1 measure within 3 months of enrollment. Mentors for arm 2 will have previously been in poor control and are now in good control, defined as having an HbA1c of > 8% in the past 3 years and an

HbA1c \leq 7.5% within 3 months of enrollment. Also, to ensure that we are targeting those most likely to benefit from improving control, participants will need to be between the ages of 30-75.

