Patients and Settings: We will enroll veterans with diabetes mellitus (DM) who receive their care from the CMC VA Medical Center (CMCVAMC). Veterans between the ages of 30 and 75 years of age -- patients most likely to reap the benefits of gaining control -- will be eligible for participation. There will be 4 arms: 1. Usual care (enrolled at two different time points); 2. Peer mentoring where mentors are veterans who were once in poor control but are now in good control; 3. Peer mentoring where the mentoring comes from former mentees from arm 2 (mentoring FFM); and 4. Former mentees from arm 2 not randomized to becoming a mentor. To ensure that we are targeting those most likely to benefit from improving control we enroll diabetics with persistently poor DM control. Persistently poor DM control will be defined as having an HbA1c > 8% on 2 different occasions in the course of 24 months, with at least 1 measure within 3 months of enrollment. Mentors for arm 2 will have previously been in poor control and are now in good control, defined as having an HbA1c of > 8% in the past 3 years and an HbA1c \leq 7.5% within 3 months of enrollment. They will also, when feasible, be the same race, sex, and age (\pm 10 years) as their mentee. When possible, if the mentee is on insulin we will seek out a mentor on insulin. These criteria for selecting both mentees and mentors have led to successful mentoring partnerships in our prior work. Patients will be identified by the Center for Evaluation of PACT (CEPACT) through VISN 4 Data Warehouse (VDW). With IRB approval, CEPACT will extract administrative, clinical, and laboratory data from the VDW on an ongoing basis. The VDW is updated regularly and thus an excellent source of up-to-date patient information. Identified patients will be sent a letter describing the study and then called. The PI has used this method to identify veterans with DM on many occasions and routinely is able enroll between 60-70% of those contacted. Potential mentors for arm 2 will be identified and approached in a similar manner. Veterans who agree to participate will be invited into the CMC VAMC to complete a consent procedure, baseline survey, and have their blood drawn to determine their HbA1c at enrollment. All enrollees and mentors will receive, regardless of the arm, \$50.00 for each visit requiring a blood draw and survey completion (baseline, 6 months, 12 months, and depending on arm, potentially 18 months).

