We will electronically create a list of CMCVAMC patients with at least two diagnosis codes for diabetes (ICD-9 code 250 and ICD 10 codes starting with E11) and at least two laboratory tests in for an HbA1c. We will exclude people if their current age is ≤ 30 and > 75 years of age. We will then review the list and determine who qualifies as a potential mentee and a potential mentor based on past HbA1c values. This will be an ongoing process.

Letters will be sent to potential participants letting them know that they may be eligible for a study with a brief description of the study and give them a number of the project manager who they can call if they would like to learn more or to request no further contact. We will also notify potential participants that if we do not hear from them we will give them a call in the following weeks. Potential mentors will be identified and contacted in a similar manner.

When patients are contacted over the phone we will give them additional description of the study and for those interested we will ask them at what age they developed diabetes. Those who indicate they developed diabetes before the age of 30 will be excluded from participating. The same will be true for when we contact potential mentors. We will also ask them about how comfortable they are with speaking English. Those who indicate discomfort with speaking English or are unintelligible over the phone will also be excluded from participating.

Those interested in participating in the study will be invited into the CMC VAMC for a face to face meeting with the study team. At that time if still interested participants and mentors will complete the consent process in person including completing a mini-quiz about the process. Those who fail the mini-quiz will be excluded from the study at that time; however, they will be reimbursed the \$50 for coming in for an in person visit. We anticipate almost everyone who comes in for a face to face visit will be entered into the study.

9.
 - 9.1. If using a clinic, be specific about who will identify the potential subject and how that information will be transmitted to the research staff.
 - 9.2. If snowball method will be used, discuss the process and how the first individuals will be recruited.
 - 9.3. Describe how information will be disseminated to subjects, e.g. handouts, brochures, flyers and advertisements (include all recruitment materials with this submission).

10. Informed Consent

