- 1.4. If chart review, breach of confidentiality is always a concern. Specify what steps will be taken to minimize these risks.

Charts will be reviewed to determine if a potential subject may be eligible for the study. Only IRB approved study personnel will access charts from VA computers during work hours. Abstraction will be limited to determine eligibility only.

Chart will also be reviewed 6 months after the last in-person visit has taken place (and for those lost to follow-up should have taken place). Minimal data will be abstract from the chart -- additional HbA1c, LDLs, and BP measurements from the time of entry into the study to the day of the chart abstraction. Only those with IRB approval will abstract this data and it will only be done on the VA premises. Data written on paper abstraction tools will be entered into the analytic database house behind the VA firewall. Paper documents will be kept on site and in locked filing cabinets in the CMC VAMC Annex.

2. Potential Study Benefits

- 2.1. Assess the potential benefits to be gained by the individual subject, as well as benefits that may accrue to society in general as a result of the planned work.

In our pilot study, poorly controlled diabetics who received mentoring on average improved their HbA1c by 1%. This is a large and clinically significant improvement. If improvements persist then the participant may reduce his or her risk of future complications from diabetes. This study in part will help us understand better if risks persist. This study has the potential also to add to our knowledge about how to better to support diabetics in general with behavioral change.

- 2.2. If the subject does not receive any direct benefit, then it must be stated here and in the consent form.

While we hope that subject will receive benefit it is likely that some participants will not benefit especially those who are randomized to usual care.

3. **Alternate Procedures**

- 3.1 Describe the alternatives available to the subject outside the research context. **N/A**
- 3.2 If none, state that the alternative is not to take part in this research study at all. **The only alternative is to not take part in the research study.**

T. **Data and Safety Monitoring Board (DSMB) or Data Monitoring Committee (DMC) (All Phase III studies are required to have a DSMB. However, the IRB has the right to require a DSMB with any study.)**

- 1. **Will an independent DSMB or DMC oversee the project?** YES NO N/A

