In order to assure 72 in each arm for stage 2, we will need a total of 144 mentees in stage 1. Again, to protect against possible attrition, we inflate that by 16% and enroll 171 mentees in stage 1. A corresponding number of mentors (171) will be recruited for stage 1. There will be no randomization of mentors in stage 1. Since usual care for stage 1 can be combined with usual care for stage 2, there is no need for a 1:1 randomization. Initially, a 1:1 randomization was used, but after evaluation we believe we can switch to a 2:1 randomization to avoid recruiting more usual care patients than necessary. With this change we will enroll approximately 139 patients to usual care in stage 1.

The combined number of poorly controlled diabetic patients receiving usual care will be approximately 195. The number of poorly controlled diabetic patients receiving peer mentoring will be 232 (171 in stage 1 and 72 in stage 2). The number of mentors in stage 1 will be 171, and the number of mentors in stage 2 will be 72 (from among those who received mentoring in stage 1). The total number of patients in the study will be 594.

A recent analysis of clinical data from the CMC VAMC and its surrounding CBOCs indicate that in the last year there were 1,248 patients who would have qualified to be mentees and 1,810 who would have qualified to be mentors.

4.2. Define plans for data and statistical analysis, including key elements of the statistical plan, stopping rules and endpoints.

For Stage 1: We will test these primary hypotheses using an unadjusted intent-to-treat analyses, i.e., with adjustment for only baseline HbA_{1c}. The primary tests will assess the significance of the coefficients associated with the treatment assignment in a longitudinal linear model of the repeated HbA_{1c} as a function of treatment, where the active group (peer mentoring) is compared to the control group via an indicator variable. Standard t-tests will determine whether a significant difference in HbA_{1c} improvement occurred between the treatment arm compared to the control arm. To account for the fact that we are doing multiple tests, we will use the Bonferroni method and consider a treatment to be significantly different than the control if the p-value is less than $0.05/2=0.025$.

| Stage 2 Analysis:

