H2. Compared to usual care, veterans who receive peer mentoring from former mentees will have improved glucose control as measured by HbA_{1c}, BP, LDL levels, DM quality of life, and depression scores: We will examine the effectiveness of the intervention at 6 months and further examine sustainability at 12 and 18 months. 18 month assessments will only be of HbA_{1c}, BP, and LDL levels as derived from the EMR. We will test these primary hypotheses using an intent-to-treat (ITT) analyses, i.e., including all patients who completed a baseline assessment, as randomized. We will use linear and random effects longitudinal models to perform the ITT comparisons at each of the follow-up visits. Our primary outcomes will be HbA_{1c}, BP, LDL levels, DM quality of life, and depression scores. Our models will include a random effect for patient. The models will include the following fixed effects: a main effect for follow-up visit (with baseline visit as the reference), intervention group, and their interactions. Tests of the interaction terms will be used to determine the ITT difference between groups with respect to change from baseline. To examine whether veterans who received peer mentoring from former mentees have improved glucose control, BP, LDL levels, DM quality of life, and depression scores compared to veterans in the usual care group at 6 months, compared to baseline, we will implement these random effects models with mentee HbA_{1c}, BP, LDL, DM quality of life score, or depression score as the dependent variable. The ITT test for effectiveness will be based on HbA_{1c} and will be two-sided, with

$\alpha=0.05$ and will be based on the magnitude and statistical significance of the time*intervention interaction term at 6 months. To examine sustainability of improvement in glucose control, BP, LDL levels, DM quality of life, and depression scores we will use the same test, but will examine the intervention group*12 month time interaction term. To examine sustainability of improvement in glucose control, BP, and LDL levels at 18 months we will again use the same test, but will examine the intervention group*18 month interaction term.

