We will check model fit by inspecting residual plots, and will assess improvement in fit with different correlation structures for the random effects. While we do not anticipate confounding in our ITT estimates because of the stratified and blocked randomization of patients, confounding due to imbalance in patient characteristics may still occur by chance. Tests for evidence of confounding will be performed by comparing baseline characteristics, between control and intervention group. Confounders will be identified as variables that are significant at the 0.20 level and we will include these as adjustment variables (fixed effects) in our analyses. These multivariable models will reduce the impact of potential bias due to confounding, as well as improve the statistical power by reducing the amount of unexplained variation in the outcome variable.

Extensive efforts will be made to collect complete information on each participant enrolled in the study. While we do not expect to be confronted with nonignorable missing data, we will nevertheless assess the sensitivity of treatment effect estimates to missing outcome data in a number of ways. We will compare the number of visits completed by participants in each arm as an additional secondary outcome, using the chi-square test. We will also compare observed characteristics of subjects with complete follow-up to those with missing data and will attempt to ascertain the reasons for missing data in subjects with incomplete follow-up.

H3: Compared to past mentees who are not randomized to becoming a mentor, past mentees randomized to becoming a mentor will have better glucose control, BP, LDL levels, DM quality of life, and depression scores: To examine whether past mentees who become mentors have better glucose control, BP, LDL levels, DM quality of life, and depression scores than past mentees who do not become mentors, the dependent variable in this analysis will be past mentee HbA_{1c}, BP, LDL level, DM quality of life score, and depression score and the intervention group will be the randomization group for former mentees. As we described above, tests of the interaction terms for each follow-up time (i.e. 6, 12 months, and 18 months) with intervention group will be used to determine the ITT difference between groups with respect to change from baseline HbA_{1c}, BP, LDL level, at each follow-up time and DM quality of life score, and depression score at 6 and 12 months.

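### The qualifying HbA1c values that every randomised patient should have on record enter no analysis, and the H2 and H3 tests do not adjust for baseline: a modest, cheaply recoverable loss of precision

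*Combined protocol and SAP*

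**What the plan says.** Mentees and usual-care patients qualify on "HbA1c > 8% on 2 different occasions in the course of 24 months, with at least 1 measure within 3 months of enrollment" (P.2.1.1, repeated in M.1.1, Patients and Settings). The source is existing laboratory data. Section P.8.1 builds a list of patients with "at least two laboratory tests in for an HbA1c", and staff then "determine who qualifies as a potential mentee and a potential mentor based on past HbA1c values". The study baseline is a separate sample: veterans who agree to take part come in and "have their blood drawn to determine their HbA1c at enrollment" (M.1.1).

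The screening values have one declared use. Section S.1.4 says of the pre-enrolment chart review: "Abstraction will be limited to determine eligibility only". Section V.2.1.2 likewise lists HbA1c levels among the existing data needed to determine eligibility. The later outcome abstraction (S.1.4) runs from study entry onward, so it does not recover them.

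In U.4.2, the Stage 1 analysis is run "with adjustment for only baseline HbA_{1c". The H2 model has a patient random effect and these fixed effects: "a main effect for follow-up visit (with baseline visit as the reference), intervention group, and their interactions". H3 follows the same form. Other covariates come in only through an imbalance screen: "Confounders will be identified as variables that are significant at the 0.20 level".

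**The concern.** Earlier values of the outcome variable are often among the most useful covariates available. Here they predate randomisation, should be nearly complete by definition of eligibility, and need no extra visit or blood draw. A single HbA1c is a noisy marker of a patient's usual level, so two further values could sharpen the comparison. The 0.20 screen would not reliably bring them in, because it selects on chance imbalance between arms and not on prognostic value. Yet U.4.2 itself names better power through less unexplained variation as a benefit of adjustment.

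A second loss sits beside this one. In H2 and H3 the baseline value is an outcome row and not a covariate. With a random intercept, the visit-by-group test is then in effect a comparison of change scores, which is less precise than baseline adjustment whenever the correlation is below 1.

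What is at stake is precision on HbA1c, chiefly for H3, the comparison with the least reserve. Neither omission causes bias or inflates the error rate.

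**Working it through.** **1. The plan's own figure.** Inputs from U.4.1: difference 0.8, SD 1.6, power 80%. Two-sided alpha 0.05 is assumed, since U.4.1 states none. n per arm = 2 × (1.960 + 0.842)² × 1.6² / 0.8² = 62.8, so 63; the t-test version gives 63.8, so 64. Power at 64 per arm is 80.1%. With 10% attrition, 64 / 0.9 = 71.1, so 72. Both stated figures reproduce, and neither takes credit for any covariate.

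**2. Which comparison that sizing covers.** U.4.1 applies 64 and 72 to Stage 1 mentees re-randomised in Stage 2, which is H3. At 0.8 and SD 1.6:
- H1, 171 v 139 at alpha 0.025: about 98%.
- H2, 72 v 195 (139 + 56, usual care pooled as U.4.1 allows): about 95%; 65 v 175 after 10% attrition: about 93%.
- H2, 72 v 56 (Stage 2 usual care only): about 80%; after 10% attrition: about 76%.

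**3. Variance factors with equal correlation r and no selection** (r is assumed, because the documents give none). Change score: 2(1 − r). Baseline adjustment: 1 − r². Baseline plus two earlier values: 1 − 3r²/(1 + 2r).

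| r | Change | Baseline | Baseline + two | Further cut |
|---|---|---|---|---|
| 0.3 | 1.40 | 0.91 | 0.831 | 8.7% |
| 0.5 | 1.00 | 0.75 | 0.625 | 16.7% |
| 0.7 | 0.60 | 0.51 | 0.388 | 24.0% |

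Moving from change to baseline adjustment multiplies variance by (1 − r²)/(2(1 − r)) = (1 + r)/2, a cut of 35%, 25% and 15% on the three rows.

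**4. Effect of selecting on values above 8%.** Simulation with assumed source mean 8.0 and SD 1.8, chart values at months −12 and −1.5 (both above 8%), baseline at month 0 and outcome at month 6. Cut in residual variance from adding both chart values to baseline:
- constant correlation 0.5: 8.0%; 0.7: 14.6%; 0.75 (the most favourable case tried): 16.9%;
- stable trait plus decay over time: about 1.4–4%;
- decay plus measurement noise: about 0.2–1%;
- pure decay over time: 0%.

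The range is about 0–15% for correlations up to 0.7. Selection also lowers the correlation between baseline and outcome in the enrolled sample: a source correlation of 0.75 becomes about 0.56. By the step 3 formula, baseline adjustment then cuts variance by (1 − 0.56)/2 = 22% against change. The chart values bring the factor to 0.78 × 0.83 = 0.65, so baseline supplies 22 of the 35 points. Across the structures tried, baseline plus chart values cut variance by about 4–38% against the change comparison.

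**5. H3 separately.** H3 is randomised at month 6 (M.1.1), so each former mentee already has study values at months 0 and 6 before that randomisation. The chart values are then 6 to 30 months old. For a month-12 outcome, beyond the month-0 and month-6 values, they removed 0% (decay plus noise), about 2% (trait plus decay) and 5–8% (constant 0.5–0.7).

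**6. Power on the plan's yardstick.** Replace SD 1.6 by 1.6 × √(1 − v) at 64 per arm. For v = 0, 5%, 10% and 15%, power is 80.1%, 82.1%, 84.1% and 86.1%. The largest gain is 86.1 − 80.1 = 6.0 points. This only indicates scale: the 80.1% uses SD 1.6 as it stands, while v is a reduction beyond baseline adjustment. U.4.1 does not say whether 1.6 is the SD of a level or of a change.

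**The case against.** The strongest reply is that this is an optional refinement. Its size rests wholly on correlations that the documents do not give, and it may be near zero: both values are selected to exceed 8%, one may be up to 24 months old, the other lies close to the baseline draw, and baseline is already used in Stage 1. All of that stands, and it is why the gain is given as a range starting at zero.

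Three stronger readings are tempting and fail.
- A reader might infer that precision is discarded without reason. Sections S.1.4 and V.2.1.2 restrict the screening values to eligibility, so they are not in the analysis data as the protocol stands. The documents give no statistical reason for leaving them out, but there is a regulatory one.
- A reader might infer that H2 and H3 are both sized at 72 per arm for 80% power. The calculation is for H3. H2 has about 95% with pooled usual care and about 80% only if its controls are the 56 from Stage 2.
- A reader might infer that the trial misses its stated power. The 64 and 72 reproduce with no covariate credit, so leaving out these values does not push the trial below them.

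It is also fair to say that the gain in H2 and H3 owes more to baseline adjustment than to the chart values. In the unselected formula at r = 0.7 the order reverses (0.60 to 0.51, then to 0.388), but selection moves the enrolled sample towards lower correlations, where baseline adjustment dominates.

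**Conclusion.** The point holds as lost efficiency. The qualifying HbA1c values are valid pre-randomisation covariates that no analysis uses, and H2 and H3 also forgo baseline adjustment. Beyond baseline adjustment, the chart values would cut residual variance by about 0–15%, or about 0–8% for H3. That is 0 to about 6 percentage points of power on the plan's yardstick (64 per arm, 0.8, SD 1.6, 80.1%). These figures depend on assumed correlation structures and an assumed source distribution; under correlation that decays purely with time the gain is nil. Baseline adjustment in H2 and H3 is the larger and more certain part. The benefit matters most for H3, least for H1, and for H2 it depends on which usual-care patients serve as controls. Nothing here shows bias or an error in the stated sample size.

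**What to change.** Before any unblinded analysis:

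1. **H2 and H3, with data already planned.** In the HbA1c models, take baseline off the outcome side and enter it as a covariate with its own coefficient at each visit. A main effect alone does not sharpen a visit-by-group test when baseline is itself an outcome row. For H3, use the month-0 and month-6 study values as the main covariates, since both precede that randomisation.
2. **Qualifying values.** Request an IRB and privacy modification so that, for consented participants, the two qualifying HbA1c values and their dates are kept in the analysis file. Amend S.1.4 and V.2.1.2 to match. State which two values count when a patient has more than two.
3. **Analysis text in U.4.2.** Prespecify baseline plus the two qualifying values as covariates in the Stage 1 model and, by visit, in H2. Treat the chart values as optional extras in H3. Do not leave them to the 0.20 screen.

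Item 1 costs a few sentences. Items 2 and 3 add two values with their dates, revised authorisation wording and one modification, which U.2.1.3 requires to be approved before it is acted on. No extra patient, visit or blood draw is needed.
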